11.4. Determination of Sample Size

It is estimated that 170 subjects per treatment group will provide 90% power with a 2-sided test at a 5% significance level and standard deviation of API at Week 12 of 2.0 to detect a treatment effect of 0.7 unit (or a standardized effect of 0.35) in change from baseline in the WAAP scores at Week 12 (Double-Blind Phase). Considering a titration success rate of 60%, this study will enroll approximately 875 subjects to obtain 340 subjects achieving a successful dose in order to be randomly assigned to study drug treatment in the Double-Blind Phase.

Additional statistical details will be outlined in the SAP.

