9.3 PRIMARY ANALYSIS

The primary analysis will be performed based on the mITT Population.

WAAPI over time will be performed by longitudinal data analysis using mixed-model repeated measures (MMRM) methods. All post-randomization baseline observations will be utilized; missing values will remain as missing (i.e. no attempt will be made to impute missing values, and only observed values will be used in the data analysis). The model will include treatment, post-baseline weeks, treatment by week interaction as fixed effects, and baseline WAAPI as the covariate. The covariance will assume to be unstructured. If the estimates do not converge, SAS default covariance structure (variance components) will be assumed. The MMRM with maximum likelihood estimation will utilize the following pseudo-SAS code for analysis:

```
proc mixed data = WAAPI Data method = ml;
class treatment week subject;
model Change in WAAPI = treatment week treatment*week baseline;
repeated week / subject = subject type = un;
lsmeans treatment / pdiff cl e;
lsmeans treatment*week /slice = week cl diff;
ods output diffs = alldiff;
```

If the estimation under type=un cannot converge, the SAS default (variance components) will be used. The estimated treatment effects, treatment differences, and the two-sided 95% confidence intervals of the treatment differences at all post-baseline timepoints will be presented. The primary comparison will be the treatment difference at Week 12.

A clear advantage of using MMRM is that this method does not require artificial missing imputations that would often create biases. The MMRM method is valid if the “missing at random” assumption holds. The trial is designed to minimize missing values: (a) Subjects who discontinue taking study medication are permitted to remain in the study, and safety and efficacy data will continue to be collected from these subjects; (b) Liberal use of rescue medication is allowed during the study, and data collection will continue even after subjects take these medications, and (c) Robust efficacy data collection procedures will be used in the trial.

Using the procedures above, it is expected that missing values will be minimal and that “missing at random” is a reasonable assumption. Therefore, the “MMRM without missing” imputation is reasonable. Sensitivity analyses of missing value imputations will be performed to support the robustness of the conclusion (see [Section 9.4](#)).

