9.4 SENSITIVITY ANALYSES

Missing values sensitivity analyses:

As the MMRM analysis does not impute missing values, sensitivity analyses with various missing value imputation methods will be performed. Sensitivity analyses based on the random replace and tipping point methods will be performed to assess the robustness of the primary efficacy data.

If all daily ratings are missing for a given week, the missing change from baseline values at a given week will be imputed using the following methods.

Random replacement method

Missing change from baseline in WAAPI at Week J will be imputed with randomly generated values from a normal distribution using a seed of 153928221. The normal distribution will be assumed to have a mean x and a standard deviation of y , where x and y are the mean and standard deviation of the changes at Week J based on all subjects (i.e., subjects from both treatment groups) with non-missing values. It should be noted that, if treatment is effective, the results of this missing value imputation method will be more conservative (i.e., biased in favor of the control).

Tipping point method

Missing change values at Week J from placebo subjects will be imputed with the value that is equal to the mean changes among placebo subjects at that week. Missing change values from active treatment subjects will be imputed with the value that is $k\%$ worse than the mean WAAPI from the placebo group at that week, where $k=0, 5, 10, 20, 30, 40 \dots 100$, until tipping (i.e., the treatment difference at Week 12 is no longer significant at a two-sided significance level of 0.05).

Additional Sensitivity Analyses:

Inclusion of paper diary data from the primary analysis

The primary efficacy variable will be analyzed including available paper diary data collected.

Exclusion of weekly average diary entries that do not have at least 5 daily entries during randomization baseline week (Week -1) and at the end of treatment (Week 12)

The primary efficacy variable will be analyzed after treating WAAPI for any giving week as missing if average pain scores are available for less than 5 days in that week.)

Exclusion of subjects who do not complete at least 4 weeks of treatment

The primary efficacy variable will be analyzed in subjects who participate in the study for at least 4 weeks of the double-blind period.

Exclusion of subjects who do not complete at least 8 weeks of treatment

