9.9 POWER AND SAMPLE SIZE JUSTIFICATION

A sample size of 170 subjects per treatment group will provide over 90% power to detect a treatment difference at a two-sided 5% significance level. In the sample size calculation, a treatment difference of 0.7 units and an SD of 2 (or a standardized effect of 0.35) for the primary efficacy variable were assumed.

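### The tipping-point analysis has no rule for carrying imputation uncertainty into its test, so its standard error is wrong: too small at k=0 and small k if placebo loses more subjects

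*SAP*

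**What the plan says.** SAP 9.3 makes the primary analysis a mixed model for repeated measures (MMRM) on observed data under missing at random, fitted by maximum likelihood: "The covariance will assume to be unstructured". SAP 9.4 supports it with two imputation-based analyses, random replacement and a tipping point. Imputation applies "If all daily ratings are missing for a given week".

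In the tipping-point analysis, a missing placebo change "will be imputed with the value that is equal to the mean changes among placebo subjects at that week". A missing active value is set k% "worse than the mean WAAPI from the placebo group at that week". k runs over 0, 5, 10, 20 and on in tens to 100, stopping when "the treatment difference at Week 12 is no longer significant at a two-sided significance level of 0.05".

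Each arm and week therefore has one fill-in constant, and both constants are built from the same estimated placebo mean. SAP 9.4 names no random draw, multiple imputation, combining rule or bootstrap for this analysis, and no model for the filled data. The only model in the SAP for this endpoint is the MMRM of 9.3. Protocol 11.3.4 adds nothing on the method.

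**The concern.** A constant fill causes two problems. The filled values have no spread, so they shrink the residual variance while counting as full observations. The sampling error of the placebo mean also enters both arms through the fill, and the test does not account for it.

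This is the only analysis in SAP 9.4 that departs from missing at random in graded steps, so the k at which it tips will be read as the measure of robustness. If the SE is too small, a statement that the result did not tip at a given k is too strong.

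Heavier placebo loss is plausible. Protocol 8.1.5 expects that placebo subjects may have more pain and need rescue medication. Protocol 8.1.4 offers withdrawal to subjects who need more than the rescue limit. Discontinuation for lack of efficacy is itself an endpoint (SAP 9.5.3).

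**Working it through.** **Inputs.** From SAP 9.9: 170 per arm, difference 0.7, SD 2, two-sided 5%. From SAP 9.4: the fill-in rule and the 0.05 criterion. Assumed, because neither document gives a figure: Week 12 missing fractions a (active) and p (placebo). Write fa = 1 − a, fp = 1 − p, n = 170, s = 2, and Ya, Yp for the observed mean changes.

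**Step 1: the plan's own figure.** SE = 2 × √(2/170) = 0.217. Then 0.7/0.217 = 3.23, and power = Φ(3.23 − 1.96) = 89.7%. This agrees with the protocol's 90%; the SAP's claim of just over 90% differs only by rounding.

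**Step 2: k=0, no true effect.** The filled active mean is fa·Ya + a·Yp and the filled placebo mean is Yp, so the estimated difference is fa(Ya − Yp).
- Actual variance: fa² × [s²/(n·fa) + s²/(n·fp)] = (s²/n)(fa + fa²/fp).
- Variance reported from the filled data: (s²/n)(fa + fp).
- SE ratio, reported to actual: √(fp/fa). Type I error: 2Φ(−1.96 × ratio).

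With a true difference, a term a·fa·gap²/n is added to both variances when the number missing is random (gap is the distance from the active mean to the fill value). It barely moves the ratio.

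Example at 20/40%: reported SE √(4/170 × 1.40) = 0.182; actual SE √(4/170 × (0.80 + 0.64/0.60)) = 0.210; ratio 0.866; type I error 2Φ(−1.70) = 9.0%.

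| Missing, active/placebo (assumed) | Ratio √(fp/fa) | SE error | Type I error |
|---|---|---|---|
| 5/10% | 0.973 | 3% too small | 5.6% |
| 10/20% | 0.943 | 6% too small | 6.5% |
| 25/35% | 0.931 | 7% too small | 6.8% |
| 20/40% | 0.866 | 13% too small | 9.0% |
| 20/45% | 0.829 | 17% too small | 10.4% |
| 20/20% | 1.000 | none | 5.0% |
| 40/20% | 1.155 | 15% too large | 2.4% |

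Simulating the filled-data test (100,000 trials per setting) reproduced these error rates to about 0.1 percentage point. A Week 12 analysis of covariance with a baseline covariate (assumed correlation 0.4, maximum-likelihood variance, 6,000 trials) gave 7.2% at 10/20%, 8.6% at 20/40% and 2.8% at 40/20%. The full multi-week MMRM was not simulated.

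**Step 3: k above 0.** Take k as a percentage of the placebo mean change, so the active fill is (1+k)Yp. The estimated difference is fa·Ya − [1 − a(1+k)]Yp, with variance proportional to fa + [1 − a(1+k)]²/fp. The reported variance stays at fa + fp, apart from the common term. The reported SE is therefore too small only while a(1+k) < p, that is, k < p/a − 1.
- 25/35%: the crossover is 0.35/0.25 − 1 = 40%. At k = 100% the ratio is √(1.40/(0.75 + 0.25/0.65)) = 1.11, so the SE is too large.
- 20/40%: the crossover is 0.40/0.20 − 1 = 100%.

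Simulation at 25/35% with fixed numbers missing, true difference 0.7 and an assumed placebo change of −1 gave ratios of about 0.93, 1.02 and 1.16 at k = 0, 40% and 100%.

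**Step 4: where it tips.** Take an observed difference of 0.7 and an assumed placebo change of −1.
- k as a percentage of the mean change, 20/30%: tips at k = 89.8% with the reported SE and 100.3% with the actual SE, which is too early.
- k as a percentage of the pain level (assumed baseline 3), 20/40%: about 24% reported and 19% actual, which is too late. On the SAP's grid this is one step, k = 30 instead of k = 20.
- The same reading at 20/30%: about 22% and 21%, which is no grid step.

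**The case against.** The strongest objection concerns reach. A tipping analysis is read at the k where it tips, and the closed form above is for k=0. A reader might infer from k=0 that the method tips too late across the whole grid and on whichever scale k is applied. Steps 3 and 4 show otherwise: on the change scale the shortfall shrinks with k and reverses once a(1+k) exceeds p. The Rubin SE gave earlier tipping than the SAP's method in every case run, but Rubin's variance is conservative here, so that comparison does not rescue the broad claim.

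A reader might also infer that the analysis cannot tip, because k stops at 100% of a placebo mean change that may be small. The documents do not support this. SAP 9.4 refers to the mean WAAPI, which is a pain level, so k = 100% could be a shift of several points. Neither document gives a placebo mean change. The result could also already be non-significant at k=0.

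Two further points stand in part. SAP 9.3 expects few missing values because subjects off drug may stay in the study, and a week is imputed only if it has no rating at all. At 5/10% the error is small. And the analysis carries no confirmatory alpha, so the primary test and the hierarchy in SAP 9.8 are untouched.

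None of this makes the constant fill correct. It limits the size and direction of the error.

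**Conclusion.** The concern holds in limited form. As written, the tipping-point test has no valid SE, and the direction of the error depends on the missing rates and on k. At k=0 and small k with heavier placebo loss the SE is too small and the result tips too late. The shortfall at k=0 runs from about 3% at 5/10% missing to 17% at 20/45%, with type I error from about 5.6% to 10.4%. Equal loss gives no error at k=0, and heavier active loss makes the test conservative there. At larger k the error can reverse.

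These sizes rest on assumed missing rates, on SD 2 and 170 per arm from SAP 9.9, and on the inference that filled values are analysed as observed. The primary analysis is not affected. The change should be made because the SAP offers this analysis as support for the primary result, and the correction is cheap.

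**What to change.** Replace the constant fill in SAP 9.4 with multiple imputation:
- Draw missing weeks from a model with baseline WAAPI and earlier weeks, using at least 100 imputations.
- Impute missing placebo weeks from the placebo model. Impute missing active weeks from the placebo model too at shift 0. This keeps the SAP's placebo-based starting point; switching to within-arm missing at random would be a separate and less stringent choice.
- Worsen the imputed active values by a fixed number of NRS points (0, 0.25, 0.5 and so on) until tipping. The shift then does not depend on the size of the placebo mean, or on whether k refers to a level or a change.
- Analyse each data set with the primary model, combine by Rubin's rules, and report the tipping shift alongside the missing rate by arm.

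The cost is a revised SAP paragraph and some extra programming. Rubin's variance is somewhat conservative in this setting, so the analysis will tend to tip a little early; the SAP should say so.

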4.4 RANDOMIZATION AND BLINDING

Randomization will be used to avoid bias in the assignment of subjects to treatment, to increase the likelihood that known and unknown subject attributes (e.g., demographics, baseline characteristics) are evenly balanced across treatment groups, and to enhance the validity of statistical comparisons across treatment groups.

During the Open-Label Titration Phase, subjects will be dosed with CAM2038 q1w until a stabilized dose and adequate analgesic effect has been achieved for at least 2 consecutive weeks prior to randomization to the Double-Blind Treatment Phase, in accordance with pre-defined randomization criteria. Subjects whose pain is controlled on 4 mg, 8 mg or 12 mg CAM2038 q1w during the Open-Label Titration Phase will be maintained on 4 mg, 8 mg or 12 mg CAM2038 q1w, or corresponding placebo, during the Double-Blind Treatment Phase. Subjects whose pain is controlled on 16 mg, 24 mg or 32 mg CAM2038 q1w during the Open-Label Titration Phase will be transitioned to CAM2038 64 mg, 96 mg or 128 mg q4w, or corresponding placebo, during the Double-Blind Treatment Phase. Subjects will be randomized to either active CAM2038 or placebo control in a 1:1 ratio within each of the q1w or q4w regimens.

Under normal circumstances, the blind will not be broken until all participants have completed treatment. In case of emergency, and only if the information is required by the Investigator to ensure subject's safety in managing a medical condition, the treatment may be unblinded at the site by using a code-break module. The code-break module will be provided by the Sponsor or designee. If possible, the Investigator should contact the Sponsor prior to unblinding and after any actions have been taken. Whenever a treatment sequence is prematurely unblinded, the reason, date and time of the unblinding, and the individual who broke the blind, must be documented. Individual code breaks will result in withdrawal of the participant from the study.

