9.2 DERIVATION OF THE PRIMARY EFFICACY VARIABLE

WAAPI scores will be calculated for each weekly interval (i.e., 7-day intervals) relative to randomization date (first randomized treatment date) for all subjects (both subjects on q1w and q4w). For example, WAAPI at Week 0 will be the average of available (non-missing) APIs captured during the 7 days prior to Treatment Day 1 (the first randomized treatment day). WAAPI at Week 1 will be the average for the next 7 days including the score captured on Day 1. WAAPI at Week 12 (the primary timepoint) will be the average for the APIs captured from Day 78 to Day 84. The baseline WAAPI score will be the WAAPI at Week 0. The changes from baseline at any post-baseline timepoint will be calculated as baseline minus post-baseline, so that a positive change is indicative of improvement.

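### The tipping-point rule in SAP 9.4 fills missing change scores on active from a placebo pain level, so the imputed value and the tipping k depend on an unstated conversion

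*SAP*

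**What the plan says.** SAP 9.4 states that, when a whole week of ratings is absent, "the missing change from baseline values at a given week will be imputed using the following methods". The quantity being filled is therefore a change score in both arms.

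For the tipping-point method, a missing placebo value is "imputed with the value that is equal to the mean changes among placebo subjects at that week". A missing active value is set k% "worse than the mean WAAPI from the placebo group at that week", with k running 0, 5, 10, 20 and so on to 100, until "the treatment difference at Week 12 is no longer significant at a two-sided significance level of 0.05".

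SAP 9.2 defines WAAPI as a weekly average of daily API scores. It defines change as baseline minus post-baseline, "so that a positive change is indicative of improvement". Protocol 9.3.1 anchors the NRS-11 at 0 and 10, so a mean WAAPI cannot be negative. Neither document converts the placebo level into a change for this step, or says which direction worse takes on the change scale.

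**The concern.** Two consecutive sentences of one rule use different scales. The placebo sentence uses a mean change, and the active sentence uses a mean level for a field that holds changes. Because positive changes are improvements, a pain level of about 4 in that field means a 4-point improvement. Making the level worse, that is higher, enlarges the improvement.

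The primary MMRM relies on missing at random (SAP 9.3), and this is the one analysis in SAP 9.4 with a penalty that escalates. Protocol 7.7 requires discontinuation for safety reasons and permits it for lack of efficacy, so outcome-related missingness is plausible. If the conversion is chosen at the programming stage, and especially after unblinding, the reported tipping k is no longer pre-specified.

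**Working it through.** **Plan's own figure.** The only numbers available for calibration are in SAP 9.9: "A sample size of 170 subjects per treatment group will provide over 90% power to detect a treatment difference", at a difference of 0.7 and SD 2. The normal formula gives n = 2(1.960+1.282)²(2/0.7)² = 171.5, so 172 per arm. Power at 170 is 0.897. That reproduces the stated figure to rounding and is not part of this point.

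**Inputs.** From the documents: 170 per arm, 1:1 allocation, SD 2, difference 0.7, two-sided 0.05. The documents do not give the Week 12 missing fraction f, mean baseline B, placebo mean WAAPI W, or the observed mean changes A (active) and P (placebo). These are assumed. W and B are kept consistent through P = B - W, and f is the same in both arms.

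**Formula.** Missing placebo values equal P, so the placebo mean stays at P. With c the value imputed on active, the difference is (1-f)A + f·c - P. P-values come from a two-sample t test with 170 per arm, counting the filled values as data. With o observed and m filled, the active variance is [(o-1)·4 + (o·m/170)(A-c)²]/169 and the placebo variance is (o-1)·4/169. This approximates the Week 12 MMRM contrast without the baseline covariate.

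**Literal rule: c = W(1+k/100).** Take f=0.3, B=3.0, W=4.2, A=-0.5, P=-1.2.
- k=0: 0.7(-0.5) + 0.3(4.2) + 1.2 = 2.11
- k=100: 0.7(-0.5) + 0.3(8.4) + 1.2 = 3.37

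The observed difference is 0.7. Protocol 7.4 requires a 7-day API of at most 4 at randomization, so no true change can exceed about +4; an imputed +8.4 is impossible. Over a grid of assumed values (B 2-4, W 2-6, difference 0.4-1.0, SD 1.5-2.5, missing 1-40%), the literal rule tipped in 0 of the 2,975 scenarios in which the observed result was significant.

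**Two sensible repairs.** Take B=3, W=4, P=-1.0, A=-0.3, f=0.2.
- Convert the level: c = B - W(1+k/100)
- Substitute the mean change: c = P(1+k/100)

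| Repair | k | c | Difference | p |
|---|---|---|---|---|
| Either | 0 | -1.0 | 0.8(-0.3) + 0.2(-1.0) + 1.0 = 0.56 | 0.004 |
| Convert level | 20 | -1.8 | 0.40 | 0.046 |
| Convert level | 30 | -2.2 | 0.32 | 0.115 (tips) |
| Mean change | 80 | -1.8 | 0.40 | 0.046 |
| Mean change | 90 | -1.9 | 0.38 | 0.058 (tips) |

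Both lose significance once c falls a little below -1.8. A 10-point step in k moves c by 0.4 under the first repair and by 0.1 under the second, hence the gap. Tipping k by missing fraction, other inputs unchanged:

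| Missing per arm | Convert level | Mean change |
|---|---|---|
| 10% | 60 | not by 100 |
| 20% | 30 | 90 |
| 30% | 20 | 50 |
| 40% | 10 | 30 |

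**Placebo mean change near zero.** Take P=-0.2, A=+0.5 (difference still 0.7) and f=0.3. Under the mean-change repair at k=100, c=-0.4 and the difference is 0.7(0.5) + 0.3(-0.4) + 0.2 = 0.43, p=0.02. The largest penalty available is 0.2 points. A fixed shift of 0.5 points gives c=-0.7, difference 0.34 and p=0.069, which tips. In the 20% case above, a shift of 0.5 gives 0.46 (p=0.020) and a shift of 1.0 gives 0.36 (p=0.074).

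**The case against.** The strongest reply is that nobody would program the literal rule. In a procedure stepped until significance is lost, worse can hardly mean more improvement. The natural reading sets the dropout's pain level k% above the placebo mean level and subtracts it from baseline. That is a demanding test: on the 30% inputs above it tips at k=10 (difference 0.36, p=0.051). The mean-change reading tips there at k=40 (difference 0.35, p=0.064).

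This much stands. A reader might infer that the analysis can never tip, or that surviving it says nothing about robustness. The documents do not support that, because either sensible repair yields a working stress test in many settings. Even with a level entered directly as a change, if worse is taken to mean a smaller change score, the rule tipped in 341 of the 2,975 grid scenarios. All 341 had placebo improving on average, whereas Protocol 8.1.5 anticipates that pain may rise on placebo.

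A reader might also infer that this is the plan's only departure from missing at random. It is not: random replacement in SAP 9.4 draws from the pooled distribution of both arms, and the SAP itself notes that this favors control if treatment works. It has no escalating penalty, however.

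Finally, SAP 9.3 expects few missing values, and the missing fractions here are assumptions. What the reply does not answer is that the SAP states neither repair and that the two disagree widely on the same data.

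**Conclusion.** The scale mismatch is real in the current text and should be corrected. Literally applied, the rule moves the estimate towards active, from 0.7 to between 2.11 and 3.37 in the 30% example. Sensibly repaired, it gives a tipping point of k=30 or k=90 on the same data at 20% missing, depending on a choice the SAP leaves open. The mean-change repair also loses force when the placebo mean change is close to zero.

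The sizes rest on assumed missing fractions, baseline and placebo means, and on a t test standing in for the MMRM; the mismatch itself rests on none of these. The consequence is confined to a supportive analysis: the primary MMRM and its significance level are untouched.

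**What to change.** Before unblinding, reword the tipping-point paragraph so that both arms are on the change scale. A missing active value at a given week equals the placebo mean change at that week minus a fixed shift in NRS points (for example 0, 0.5, 1.0 and so on), increased until the Week 12 p-value exceeds 0.05. State that worse means a smaller baseline-minus-post value. An additive shift has a defined sign whether placebo improves or worsens, keeps its force when the placebo mean change is near zero, and reports the tipping point in units a clinician can judge.

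Multiple imputation combined by Rubin's rules is an optional refinement, so that filling gaps with a constant does not understate variance; correcting the mismatch does not require it.

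The cost is SAP wording and modest programming. SAP 6.2 already provides version numbering for revisions after the final version.
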